Primary hypothesis: Subjects who are in the active ABM group will exhibit less tendency for stress related (state) rumination compared to those in the placebo group (2 weeks). Active vs placebo ABM will decrease depressive symptoms (6 months) and this effect will be mediated by the change in state rumination. Densely connected symptom network and high strength centrality of rumination at baseline will moderate the effect of ABM. See figure 3.

[figure not shown]

Figure 3. Model of the primary hypothesis

Secondary hypotheses: After the intervention, patients with changes in affective bias after ABM develop a less densely connected symptom network and have reduced strength centrality of rumination. Reduced network density and reduced strength centrality of rumination after ABM leads to reduction in depressive symptoms at 6 months.

4. Project methodology

Design and participants. The Affective Bias Modification Task (ABM) will be applied in a randomized controlled, double blind clinical trial with 6 months follow-up. Personalized networks

are generated from prospective assessment of depression-related processes at baseline and follow-ups, allowing us to investigate for whom this procedure is effective. Patients (N = 150) will be recruited from an out-patient clinic at Diakonhjemmet Hospital, and randomized into one of three conditions: active, sham and assessment only. Patients aged 18-65 with depression (major depressive disorder) or bipolar disorder 2, with or without comorbid anxiety and/or alcohol use disorder will be included. Exclusion criteria are a history of mania, psychosis, or a neurological disorder.

4.1. Project arrangements, method selection and analyses.

Negative affective bias. In the dot-probe task (MacLeod et al., 2002) paired stimuli (e.g. a negative and a positive face) are presented, followed by one or two probes (dots) appearing in the spatial location of one of the stimuli. See figure 4. Participants are then required to press one of two buttons as quickly as possible to indicate the number of dots in the probe. Thus, if the participant systematically orients towards a negative emotional stimulus (i.e. has a negative affective bias), they respond faster to probes presented at the spatial location of the negative stimulus compared to probes at the location of the positive stimulus. Stimuli

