presentation time is 50% 500 ms and 50 % 1000 ms (evenly distributed throughout the task). In total, the dot probe task will comprise 90 trials of paired images of faces of different valences.

The Facial Expression Recognition Task (FERT; (Harmer, O'Sullivan, et al., 2009) is another measure of negative affective bias and is included to make sure that biases measured with the dot probe task transfers to an independent measure. In this task, pictures of faces are gradually morphed between neutral, and positive and negative facial expressions. The detection threshold for correctly identifying the facial expression is the variable of interest.

Affective bias modification. The task is almost identical to the dot probe task. The differences are that the probe appears at the location of the most positive stimuli of each pair in 87 % of trials (encouraging a positive affective bias). In the control condition, there is no contingency between facial expressions shown and the probe location. Participants will do ABM in their homes (approx. 5 min.) twice a day for two weeks (28 sessions) using laptop computers provided by us. Our experience with previous ABM studies indicate good adherence by participants using this regime.

EMA of affective symptoms. The estimation of the each participant's symptom network is based on data from three separate two-weeks of EMA (baseline, follow-up and six months), conducted by means of the PsyMate™-app on their smartphones. The app pings four times per day (in the morning, middle of the day, afternoon, evening), at slightly irregular intervals, and instructs the participant to report on mood and symptoms guided by Positive and Negative Affective Schedule (PANAS; (Thompson, 2007)) and DSM-5 criteria of MDD, respectively, and the extent they have been engaged in brooding rumination. In total, the participant is pinged 56 times per two-week period and each self-report takes approximately 1 minute to complete.

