Negative mood induction paradigm. Drawing on diathesis-stress models of affective disorder (Disner, Beevers, Haigh, & Beck, 2011), we will include a negative mood-induction procedure prior to assessment of state rumination and stress reactivity (Westermann, Stahl, & Hesse, 1996). A standardized mood induction script, personalized by stressful autobiographical events (Sinha & Tuit, 2012), will be recorded for each patient. Upon listening to the script, they are asked to imagine themselves being in the situation. Imagery vividness scale (Sinha & Tuit, 2012) is used to assess how clear they manage to imagine themselves in the situation. Afterwards, subjects will be left alone for five minutes to trigger state rumination. A shortened version of the Profile of Mood States (POMS; 37 items) will be administered before and after the mood induction as a manipulation check (Shacham, 1983). Our research group have previously shown that POMS reflects changes in mood states over short intervals in healthy controls (Walderhaug et al., 2007). Stress reactivity is operationalized as reduced HRV (measured via the Polar RS800 heart rate monitoring system) and rising cortisol levels (measured via Salivette® saliva sampling). A meta-analysis of cortisol response after stress induction has shown that peak cortisol is reached 38 minutes after stress induction onset (Goodman, Janson, & Wolf, 2017). Between post-induction and recovery, the participants will be encouraged to watch emotionally neutral videos (selected National Geographic films). See figure 6 for procedure and time schedule.

[figure not shown]

Figure 6. Negative mood induction procedure. BSRI = Brief state ruminative inventory. HRV = Heart rate variability. POMS = Profile of mood states.

Statistical power. Calculation of statistical strength regarding detecting an effect of ABM is based on an assumption that 20 % in the placebo group will report 3 points improvement on BDI-II at follow-up compared to 50 % in the active ABM group. The National Institute for Health and Care Excellence (NICE, 2009) , suggests a difference of ≥ 3 BDI-II points is a clinically significant treatment effect for depression. By assuming 15 % drop-out at follow-up, 50 patients in each condition (total n= 100) will be required when $1 - \beta = .80$ and $\alpha = .05$. The literature provides no clear guidelines as to how many data points that is necessary to reliably estimate a patient's

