symptom network, but simulation studies suggest adequate performance for estimating an eight-node network using 50 observations (Epskamp et al., 2018). Given multiple regression analysis with up to six predictors and a small effect size ($<.10$), $\beta = .80$ and $\alpha = .05$, the estimated required sample size is 81. When examining the effect of ABM, we are only interested in effect sizes of clinical relevance (i.e. < 0.25). Given an ANOVA repeated measures analysis with effect size = 0.25, $\beta = .80$ and $\alpha = .05$, the estimated required sample size to detect a difference in changes in the network metrics between the conditions is 34.

Mediation and moderation analysis. The mediation analysis, investigating whether the relation between ABM and symptoms change is mediated by rumination, will be performed according to the procedure established by Baron and Kenny (1986). The moderated mediation analysis, investigating whether ABM changes depressive symptoms as a function of symptom network, will be performed according to recommendations made by Muller, Judd, and Yzerbyt (2005).

Feasibility. Labs for conducting the research are available at the Department of psychology, University of Oslo. The biobank “Genes in cognition and Emotion” REK SørØst 2011/2593 will be used to store salvia samples. Twenty-five laptop computers for conducting the ABM-intervention and Polar watches for recording HRV are already acquired. Neurocognitive labs are available at the Department of Psychology. All questionnaires are translated into Norwegian by means of back translation procedures. The negative mood induction procedure will be piloted before commencement. The project is currently under evaluation by REK SørØst 2019/330. During the last decade, through our longstanding collaboration with Diakonhjemmet Hospital and other nearby clinics, we have managed to recruit hundreds of patients in different stages of their depressive illness to take part in clinical studies. The TSD (in Norwegian, Service for Sensitive Data) service will be used for storing and post-processing sensitive-data in compliance with the Norwegian “Personal Data Act” and “Health Research Act”. TSD is developed and maintained by USIT at the University of Oslo and supports research activities run at Norwegian public institutions.

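### Does the regression figure of 81 patients leave the network moderators underpowered because it ignores their measurement error?

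*Combined protocol and SAP*

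**What the plan says.** All places are in the combined protocol and SAP.

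- Section 3 (primary hypothesis): "Densely connected symptom network and high strength centrality of rumination at baseline will moderate the effect of ABM". The effect in question is active versus placebo ABM on depressive symptoms at 6 months.
- Section 4, Design and participants: 150 patients are "randomized into one of three conditions: active, sham and assessment only".
- Section 4.1, EMA of affective symptoms: "In total, the participant is pinged 56 times per two-week period". The items cover mood (PANAS), DSM-5 depression criteria and brooding.
- Section 4.1, Statistical power, main comparison: "By assuming 15 % drop-out at follow-up, 50 patients in each condition (total n= 100) will be required".
- The same paragraph admits that the literature gives "no clear guidelines as to how many data points that is necessary to reliably estimate" a patient's network, and then relies on the statement that "simulation studies suggest adequate performance for estimating an eight-node network using 50 observations".
- The next sentence begins "Given multiple regression analysis with up to six predictors and a small effect size" and arrives at 81 patients. It does not name the regression. A separate figure of 34 follows, and that one is explicitly for change in the network metrics.
- Section 4.1, Mediation and moderation analysis: a moderated mediation analysis is planned, "investigating whether ABM changes depressive symptoms as a function of symptom network".
- Graphical vector autoregression appears once, as an example, in the Introduction.

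**The concern.** The moderators are not questionnaire totals. Each is a summary of a model fitted to one person's two-week diary, so it carries estimation error. Error in a moderator weakens its apparent interaction with treatment. The 81 comes directly after the sentence on network estimation, so it is natural to take it as the sample size for the moderation test. It then seems to have almost no slack against the 85 active and sham patients expected after drop-out.

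The cited benchmark concerns recovery of a network. It does not say how well density or centrality ranks people. The methods also give no node list, no lag or overnight rule, no expected response to prompts and no estimator settings.

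Two things would be at stake. A null moderation result could be misread as evidence that network features do not identify who benefits. And choices left open until data are seen could give analysts too much freedom in a test that belongs to the primary hypothesis.

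**Working it through.** **Inputs.** From section 4.1: six predictors, effect size .10 (printed as less than .10, metric not named), alpha .05, target .80, result 81. The target is printed as beta, but the main calculation in the same paragraph writes it as 1 − beta, so this is a clerical slip. Also from section 4.1: 100 active and sham patients, 15% drop-out, 56 prompts, eight nodes, 50 observations. Reliability is not in the documents and is varied here as an assumption.

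**1. Reproducing 81.** Test one coefficient with a noncentral F: numerator df 1, denominator df N − 7, noncentrality f²·N with f² = .10.
- N = 80: power .797. N = 81: power .802. So 81 reproduces exactly.
- Other readings do not give 81. The joint test of six predictors needs 143, a one-sided test 64, and R² = .10 (f² = .111) needs 73.

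**2. Patients available.** 100 × 0.85 = 85. The plan states the 15% for follow-up and lists six months as a separate wave, so using 85 for the 6-month outcome is an assumption. At N = 85 the formula gives power .821, so the plan's own figure is met.

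**3. Adding error, by formula.** If .10 is the effect of an error-free moderator, reliability R reduces f² to about .10·R. At N = 85, power is .80 at R = .95, .73 at .8, .53 at .5 and .35 at .3.

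**4. Adding error, by simulation.** The formula treats predictors as fixed. A treatment-by-moderator product is random, so the test was also simulated directly: N = 85, six predictors, two-sided alpha .05, interaction f² = .10. Repeat runs differ by a point or two.

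| Reliability | Formula | Simulation |
|---|---|---|
| 1 | .82 | .78 |
| .95 | .80 | .75 to .76 |
| .8 | .73 | .67 to .69 |
| .5 | .53 | .47 to .48 |
| .3 | .35 | .31 |

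For the interaction test, no reliability reaches .80 at N = 85. A threshold of .95 is therefore a product of the formula and should not be quoted as a requirement.

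**5. The other reading of .10.** Effect sizes in such calculations are ordinarily those expected for the variable as analysed. Then 81 needs no correction. The implied error-free effect is simply larger: at R = .5 it is .10 / .5 = .20. The plan does not say which reading it intends.

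**6. Data per network.** 4 × 14 = 56 prompts, which exceeds the cited 50. Reaching 50 needs 50/56 = 89% response. Lag-1 pairs number at most 55, or 3 × 14 = 42 within days. An eight-node model has 64 temporal and 28 contemporaneous parameters, 92 in all. That should not be set against 55: each pair supplies eight outcome values, so 55 × 8 = 440 values are available, and each temporal equation has eight slopes.

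**7. Does 81 drive recruitment?** No. The 50 per arm comes from the 20% versus 50% responder comparison. The standard formula gives 39 per arm, and 39/.85 rounds up to 46, or 53 with a continuity correction (45/.85). The 81 is only a secondary check on that number.

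**The case for a change.** The strongest contrary case does not depend on any particular reliability. Density and centrality from a two-week diary are certainly imperfect, and the plan itself admits the lack of guidance. Even mild error takes the simulated power further below .80. If 81 does not belong to the moderation test, then no sample size is given for that part of the primary hypothesis. And the open choices of nodes, lags and edge type each alter the metric.

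Much of this stands as description. Power for moderation is probably modest, the model behind 81 is unnamed, and network details are missing from the methods. The text between Feasibility and section 4.4, and the figures, were not available for this check.

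The step to a required change does not stand. The link between 81 and the moderators rests on adjacency. The secondary hypothesis, in which change in network metrics predicts 6-month symptoms, or the mediation analysis could equally be the regression meant. How far below .80 the power would fall depends on edge sizes and person-to-person variation that the documents do not give, so any figure would be the critic's own. Error in a baseline metric is also unrelated to randomised arm. It pulls the interaction toward zero and does not create a false one. The concern about analyst freedom is fair, but it is met by writing the choices down before fitting. It does not show that any stated rule is wrong.

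**Conclusion.** The concern does not call for a change. The plan's figure of 81 is correct for a single-coefficient test at f² = .10, and 85 patients exceed it. A shortfall appears only if three things are assumed together: that 81 was meant for the moderators, that .10 is the effect of an error-free moderator, and that the 15% drop-out also holds at 6 months. Under those assumptions, power is about .78 with no error at all and about .68, .48 and .31 at reliability .8, .5 and .3. The documents support none of these reliabilities over the others.

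The missing network detail is a gap that analysts fill sensibly. The item domains, the graphical vector autoregression named in the Introduction and the eight-node benchmark point to a conventional specification that can be settled before outcomes are examined. The 56 prompts exceed the benchmark the plan cites and are a fair trade against patient burden. Recruitment was set by the responder comparison, so restating 81 would alter no sample size, visit or analysis. A moderation estimate read with its confidence interval already protects against taking a wide null as proof of no moderation, and no advance label for null results is needed.

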Official title of study:

A Personalized Approach to Effects of Affective Bias Modification on Symptom Change and Rumination

NCT04137367

Date: September 23rd 2019

1. *A personalized approach to effects of affective bias modification on symptom change and rumination. A randomized controlled trial.*

2. Introduction.

A main objective of this project is to investigate whether transdiagnostic rumination mediates the effects of affective bias modification on depressive symptoms. By combining general mechanisms research with a personalized symptom network approach, we will be in the forefront of understanding how a drug-free treatment option works and for whom it works best.

There is a growing consensus that the traditional approach to mental disorders in psychopathology research is constraining new scientific discoveries. Up until recently, research has been guided by the idea that a specific constellation of psychiatric symptoms reflects a specific psychiatric disorder, and that a specific pathogenic pathway causes this. However, findings based on this approach have not aligned with findings from clinical neuroscience and genetics, is poor in predicting treatment response, and does not seem to capture the underlying mechanisms of dysfunction (Insel et al., 2010). The problem is particularly disturbing for depression research, as depression is a very heterogenic disorder (Goldberg, 2011) with numerous plausible etiological and maintaining pathways (Charney & Manji, 2004; Wittenborn, Rahmandad, Rick, & Hosseinichimeh, 2016) and high levels of comorbidity (e.g., anxiety and alcohol use disorder; (Brown, Campbell, Lehman, Grisham, & Mancill, 2001; Kessler et al., 1997).

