Clinical and cognitive assessment. Diagnostic assessment will be made in accordance with the MINI International Neuropsychiatric Interview PLUS 5.0.0 (Sheehan et al., 2006). Depression symptoms will be assessed using Beck Depression Inventory – II (BDI-II; (Beck, Steer, & Brown, 1996)). Anxiety symptoms will be assessed using the Beck Anxiety Inventory (BAI; (Beck, Epstein, Brown, & Steer, 1988)). Trait rumination will be assessed by means of the Rumination Response Scale (RRS; (Treynor, Gonzalez, & Nolen-Hoeksema, 2003)). State rumination will be assessed by means of the Brief State Rumination Inventory (BSRI; Marchetti, Mor, Chiorri, & Koster, 2018)). General attentional control will be assessed by the Attention Network Test (ANT; Fan, McCandliss, Fossella, Flombaum, & Posner, 2005)).

[figure not shown]

Figure 4. Dot probe

[figure not shown]

Figure 5. Design, procedures and schedule. ABM = Attention Bias Modification. AUDIT = Alcohol use disorder identification test. BAI = Beck Anxiety Inventory. BDI-II = Beck Depression Inventory - Second Edition. DUDIT = Drug use disorder identification test. EMA = Ecological Momentary Assessment. FERT= Facial expression recognition task. MINI = MINI International Neuropsychiatric Interview PLUS 5.0.0. RSS = Ruminative response scale.

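### Mediation by state rumination is part of the primary hypothesis, but its only stated method is a cited causal-steps procedure, with no indirect-effect estimate, interval or power written out

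*Combined protocol and SAP*

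**What the plan says.** The Introduction (section 2) states: "A main objective of this project is to investigate whether transdiagnostic rumination mediates the effects of affective bias modification on depressive symptoms". Section 3 puts the same idea in the primary hypothesis: "Active vs placebo ABM will decrease depressive symptoms (6 months) and this effect will be mediated by the change in state rumination". The first sentence of that hypothesis places state rumination at 2 weeks, and section 4.1 (Clinical and cognitive assessment) names the instrument: "State rumination will be assessed by means of the Brief State Rumination Inventory".

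The method is one sentence under Mediation and moderation analysis in section 4.1, which says that the mediation analysis "will be performed according to the procedure established by Baron and Kenny (1986". A second citation covers moderated mediation. The readable text gives no equations, covariates, indirect-effect estimate, interval or decision rule.

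The Statistical power paragraph gives three sample sizes: 50 per condition, from the assumption that "20 % in the placebo group will report 3 points improvement on BDI-II at follow-up compared to 50 % in the active ABM group"; 81 for a multiple regression with up to six predictors; and 34 for change in network metrics. None is described as power for mediation.

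The part of the document between sections 4.1 and 4.4 was not available to this review, nor were the figures. Every statement that something is absent is limited to the readable text.

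**The concern.** A main objective could be answered without saying how large the pathway is or how precisely it is known. As causal steps are usually run, the analyst first needs a significant total effect of arm on outcome, then a significant arm effect on the mediator, then a significant mediator effect on outcome. If the first test fails, the analysis stops and nothing is reported on the pathway. If all pass and the direct effect is not significant, the result is often labelled full mediation. These rules are an assumption here, because the plan cites the procedure and does not list its steps.

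The plan also does not state the assumption that any such analysis needs: no unmeasured common cause of 2-week rumination and 6-month symptoms. Randomisation protects the arm comparison, but not the link from mediator to outcome.

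**Working it through.** **1. The plan's own sample sizes.**
- 20 vs 50%, two-sided 0.05, power 0.80: n = [1.96·√(2·0.35·0.65) + 0.8416·√(0.2·0.8 + 0.5·0.5)]² / 0.30² = 38.5, so 39 per arm, and 39/0.85 = 45.9, so 46. With continuity correction, 45 and 45/0.85 = 52.9, so 53. Fisher's exact test needs 44, and 44/0.85 = 51.8, so 52. The stated 50 is within this range.
- 81: reproduced as a test of one coefficient with f² = 0.10. The test of all six predictors together would need 143.
- 34: reproduced for two groups and two time points, f = 0.25, correlation 0.5 (assumed).

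None of these is for a product of two paths.

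**2. Inputs for the check.** Analysed per arm: 50·0.85 = 42.5, taken as 42. This assumes that the 15% drop-out, stated at follow-up, applies at 6 months; the EMA paragraph lists follow-up and six months separately. Planning effect on a latent normal scale: z(0.5) − z(0.2) = 0.84 SD, also assumed to apply at 6 months. Path sizes are not in the plan and are assumed: a is the arm effect on rumination in SD units, b the slope of outcome on rumination.

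**3. Model.** With arm X = 0/1, and signs set so that positive means benefit: M = aX + e₁; Y = (d − ab)X + bM + √(1 − b²)·e₂, with standard normal errors. The total effect is d and the within-arm SD of Y is 1. Steps: total, a and b tests all p < 0.05, and direct effect smaller than total. CI: the Monte Carlo 95% interval for ab excludes 0. Simulated percentages carry an error of about a point.

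**4. Planning effect, d = 0.84.** Direct share is 1 − ab/0.84.

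| a | b | Direct share | Steps | CI |
|---|---|---|---|---|
| 0.40 | 0.4 | 81% | 41% | 43% |
| 0.62 | 0.4 | 70% | 77% | 79% |
| 0.84 | 0.4 | 60% | 91% | 94% |
| 0.84 | 0.5 | 50% | 93% | 96% |

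The two methods differ by 2 to 3 points. A full-mediation label would appear in about 4% of trials in the first row, 15% in the second and 44% in the last, although half or more of the effect is direct in each.

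**5. True difference of 3 BDI-II points.** The power paragraph cites guidance that a "difference of ≥ 3 BDI-II points is a clinically significant treatment effect for depression". The SD is not given; 8 to 12 is assumed. With d = 3/SD and noncentrality d/√(2/42):

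| SD | d | Noncentrality | Total effect significant |
|---|---|---|---|
| 8 | 0.375 | 1.72 | 40% |
| 10 | 0.30 | 1.37 | 27% |
| 12 | 0.25 | 1.15 | 20% |

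With baseline values in the models (correlation 0.5 assumed) this rises to about 26 to 51%. In the remaining trials the steps report nothing on the pathway. Unadjusted, with b = 0.4, steps against CI are 35 vs 78% (SD 8, a 0.62), 17 vs 77% (SD 12, a 0.62), 22 vs 42% (SD 8, a 0.40) and 8 vs 22% (SD 12, a 0.25). Requiring both the CI and the total effect gives the same percentages as the steps. Median CI widths are about 3.1 to 5.1 BDI-II points, for true indirect effects of 1.2 to 3.0.

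**6. Power for the pathway alone.** With 84 analysed, the joint test of a and b has 21% power at a 0.3, b 0.3; 49% at 0.5, 0.3; and 95% at 0.8, 0.5. For 80% power, about 372, 146 and 92 analysed patients are needed at a 0.3, 0.5 and 0.8 with b 0.3.

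**7. False support.** Suppose rumination has no effect and early mood E = 0.84X + e drives both M and Y with loading 0.6 or 0.7. The CI read alone then declares mediation in about 59% and 77% of trials, against 42% and 63% for the steps. In two cases without mediation (a 0.84, b 0; and a 0, b 0.5; both d 0.84), requiring a significant CI and total effect without a direction condition gives about 5% false support, against 2.2 to 2.4% for the steps. A same-sign condition brings it to 2.3 to 2.7%.

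**The case against.** The strongest objection is that the plan's citation is itself a specification, and that the total-effect gate and the full-mediation label appear nowhere in the text. It stands in part. The gate and the label are assumptions about usual practice, and the cited source may contain more. But the citation does not settle covariates, interval or reporting for this trial, and that gap does not depend on how the source is read.

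A reader might infer that the mediator is undefined, because the analysis sentence says only rumination and section 4.1 lists a trait scale as well ("Trait rumination will be assessed by means of the Rumination Response Scale"). The documents do not support that. Section 3 names state rumination, 2 weeks, symptoms at 6 months and active against placebo, and section 4.1 assigns the BSRI to state rumination.

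A reader might take the figure of 81 as covering mediation. It is not labelled so, and it fits a test of one coefficient.

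The section 3 claim needs a symptom effect in any case, so a joint rule has no more power than the steps. That stands in full. So does the point that an ungated interval gives more false mediation under confounding.

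**Conclusion.** The point holds as a specification and reporting gap on a primary claim, and is worth correcting. At the plan's own effect, replacing the steps barely changes how often mediation is detected; what it adds is a size and an interval. If the true difference is nearer 3 BDI-II points, the steps would leave the pathway unreported in about 60 to 80% of trials (100 less 40 and 20%). This rests on the usual causal steps, 42 analysed per arm at 6 months and SDs of 8 to 12.

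Three stronger readings are tempting and not supported. That the trial is underpowered for mediation cannot be shown, because the plan states no path sizes and power runs from 21 to 95% over those tried. That the cited procedure would miss most true mediation (17 vs 77%) needs an effect below the planning effect and, in that case, a pathway carrying almost all of it: 0.62·0.4·12 = 2.98 of 3 points. That full mediation will be wrongly declared depends on a label that the plan does not use, with a rate from 4 to 44%.

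**What to change.** Under Mediation and moderation analysis, replace the causal steps with one prespecified model:
- Contrast active vs sham; mediator 2-week BSRI; outcome 6-month BDI-II; baseline BSRI and baseline BDI-II in both models. A baseline BSRI is inferred from the hypothesis about change in state rumination, since the schedule figure was not available.
- Report the indirect effect as a product of coefficients, in BDI-II points, with one named 95% CI (percentile bootstrap or Monte Carlo), whether or not the total effect is significant. Report the total effect and its CI beside it.
- Call the section 3 joint hypothesis supported only if both are significant and both are in the direction of benefit.
- Do not use full or partial mediation labels.
- State the assumption of no unmeasured confounding between mediator and outcome.
- Give mediation power for named path sizes, or say that mediation is not powered.

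The cost is SAP wording and a few lines of standard code, with no added measure if the baseline BSRI is taken as inferred. The downside is that the interval may be read alone, with the higher false-mediation rates shown above; the joint rule guards against that at no gain in power.
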